#### **7.4 Safety Set**

The Safety Set will include all subjects with at least one eye implanted with a study lens. Summaries and analyses based on the Safety Set will analyze subjects as treated.

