### 5.3 REASONS NOT TO IMPLANT A STUDY IOL

At the time of cataract surgery, but prior to IOL implantation there are operative adverse events that may prevent implantation of the designated IOLs for this clinical study. These criteria include, but are not limited to:

- 1) Intraoperative complications during the phacoemulsification and IOL implant that require any other additional procedures or further intervention
- 2) Significant detachment of Descemet's membrane
- 3) Significant corneal endothelial damage
- 4) Wound burn
- 5) Capsular tear, iris incarceration or damage, posterior capsular rupture, vitreous loss or prolapse, or zonular weakness, dehiscence or rupture
- 6) Significant anterior chamber bleeding
- 7) Excessive iris mobility or need for iris manipulation
- 8) Mechanical or surgical manipulation required to enlarge the pupil prior to or at IOL implantation
- 9) Other ocular conditions or complications that could compromise IOL stability
- 10) Bag sulcus, sulcus-sulcus or unknown placement of haptics
- 11) Any method of anterior capsulotomy other than circular continuous capsulorhexis (e.g., anterior capsular tears or any areas of 'can-opener' capsulotomy or FLACS)
- 12) Capsular fibrosis or other opacity
- 13) Optic and/or haptic damage/amputation
- 14) Inability to fixate IOL in desired position

If an operative adverse event prevents implantation of the investigational IOL in the first eye and the IOL did not touch the eye, the subject should be implanted with a non-study IOL instead and discontinued from the study, followed under the Investigator's normal standard of care.

If an operative adverse event prevents implantation of the investigational IOL in the first eye and the IOL touched the eye, the Investigator should follow the subject through resolution of any adverse events (AEs) and then discontinue the subject. If an operative AE prevents implantation of the investigational IOL in the second operative eye, the Investigator should follow the subject through resolution of any AEs for the second operative eye and the subject should remain in the study and attend all study visits for the first operative eye.

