## 8.7.2 DEFINITION OF SERIOUS ADVERSE EVENTS

A serious adverse event (SAE) is defined as any untoward medical occurrence that meets any of the following:

- Is associated with a loss of 2 or more lines of BCDVA [loss of 10 or more Early Treatment Diabetic Retinopathy Study (ETDRS) letters] at Visit 4 or later from any prior postoperative visit
- Requires inpatient hospitalization or prolongation of existing hospitalization;
- Requires medical or surgical intervention to preclude permanent impairment of a body function or permanent damage to a body structure;
- Is life threatening (places the subject at immediate risk of death from the event as it occurred) or sight threatening;
- Results in permanent impairment of a body function or permanent damage to a body structure;
- Results in death;
- May jeopardize the subject and require medical or surgical intervention to prevent one of the other outcomes.

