#### 8.7.5 ADVERSE EVENT REPORTING

All AEs that occur during or after the Preoperative Visit through completion of study participation must be documented. Adverse events are collected from time of informed consent, and may be determined by evaluating the following in relation to the study subject:

- Observed or volunteered problems
- Complaints
- Physical signs and symptoms
- The occurrence of a medical condition during the study, which was absent at baseline
- The worsening of a baseline medical condition during the study

Each subject eye must be examined for the presence/absence of adverse events at all visits, whether scheduled or not. If an AE occurs, the first concern will be the safety and welfare of the subject; treatment should be provided as appropriate for the event.

AEs, regardless of causal relationship, must be assessed by the Investigator and recorded in the subject's CRF. AEs should be recorded in the form of a diagnosis, rather than signs and symptoms. Each AE must be described as ocular or non-ocular along with the following information: date of onset, date of resolution, severity, nature of the event (intermittent, continuous), action taken (none, medical and/or surgical), relationship to study device and surgical procedure, seriousness criteria and expectedness. Any medication or other intervention necessary for the treatment of an AE must be recorded on the appropriate eCRF. If the same type of AE occurs multiple times, each event should be recorded separately.

AEs will be documented beginning at the time of onset, and documentation must continue until recovery is noted. Events that are ongoing at the time of study exit should be followed until resolution or stabilization.

Ocular conditions or diseases noted during the Preoperative Visit that are chronic but stable and meet the inclusion/exclusions criteria should be recorded as Ocular History in the subject's case report form.

The worsening of a preoperative condition or disease will be considered an AE. As applicable, signs and symptoms indicating a common underlying pathology should be noted as one comprehensive event.

---

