## 7.2 All-Implanted Analysis Set

The All-Implanted Analysis Set (AAS) will include all subjects (eyes) with successful IOL implantation with at least one postoperative visit. Summaries and analyses based on the All-Implanted Analysis Set will analyze subjects as treated.

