## 9. Disposition of Subjects

The total number of screened subjects and screen failures prior to randomization will be presented. The number of subjects randomized as well as the number and percentage of subjects with at least one eye implanted with an IOL and subjects not implanted with an IOL will be presented by treatment group and overall. Inclusion in the ITT Set, All-Implanted Analysis Set, Best Case Set, Safety Set, [REDACTED]

[REDACTED] as well as study completion status will be summarized by treatment group and for all subjects using discrete summary statistics. The number of discontinuations and reasons for discontinuation will be summarized by treatment group and for all subjects using discrete summary statistics. A subject listing will be provided which includes the study exit date, study completion status, and the reason for premature study discontinuation (if applicable).

In addition, the prevalence of any protocol deviations, major protocol deviations, and minor protocol deviations will be summarized by treatment group and for all subjects using discrete summary statistics. A subject listing will be provided for protocol deviations which will include the date of the deviation, the visit at which the deviation occurred, the deviation code, the deviation description, action taken in response to the protocol deviation, and the classification of whether the deviation was judged to be major or minor in a masked review.

Subject accountability at each of the post-operative visits will be summarized overall for all subjects and by treatment group for first operative eyes and second operative eyes using discrete summary statistics, based on Table A.1 from ISO 11979-7.

Details of the study randomization, including the first eye to be implanted, randomization number, randomization date, randomized treatment, and actual treatment, will also be included within a subject listing.

A subject listing indicating whether a subject met all eligibility criteria, was a screen failure, the screen failure date (if applicable), and the eligibility criteria not met (if applicable) will also be provided.

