## **12. Operative Procedures**

Operative procedure data will be recorded at the operative visit for each eye. The operative parameters include incision size (mm), incision axis (degrees), incision type (corneal, limbal, other), lens extraction method (phacoemulsification, other), capsulotomy shape (continuous curvilinear capsulorhexis, other), position of the haptics (in the bag, partially in the bag, in the sulcus, uncertain), IOL power, whether the subject experienced any intraoperative complications, and whether any SSIs were performed.

Operative procedure variables will be summarized at the eye level by treatment group using discrete or continuous summary statistics, as appropriate, for the Safety Set. A listing of the operative variables will also be provided for each subject for each eye.

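### Subjects whose first eye was touched by the study lens but not implanted because of an operative adverse event fall outside every visible by-arm safety rate

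*SAP*

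**What the plan says.** SAP 7.4 defines the population for safety: "The Safety Set will include all subjects with at least one eye implanted with a study lens". Protocol 9.3 says the same. SAP 7.4 adds that subjects are analysed as treated.

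Protocol 5.3 splits first-eye cases in which an operative adverse event prevents implantation.

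- **Lens did not touch the eye:** "in the first eye and the IOL did not touch the eye, the subject should be implanted with a non-study IOL instead", and the subject leaves the study for routine care.
- **Lens touched the eye:** the rule reads "in the first eye and the IOL touched the eye, the Investigator should follow the subject through resolution of any adverse events", after which the subject is discontinued. No second-eye study implant is therefore planned.

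Protocol 5.4 and 7.1 class a subject who leaves before first-eye implantation as a screen failure. Protocol 7.1 also allows randomized subjects who do not receive a study IOL to be replaced.

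On data collection, Protocol 8.7.5 says "Adverse events are collected from time of informed consent". SAP 15.3 counts an ocular event as treatment-emergent if it occurs or worsens during or after the operation on that eye. It does not require implantation.

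SAP 15 and Protocol 9.4.6 make the Safety Set the default for all safety analyses. The operative data in SAP 12, which record "whether the subject experienced any intraoperative complications, and whether any SSIs were performed", are also summarized on that set. SAP 9 states that the number of "subjects not implanted with an IOL will be presented by treatment group and overall".

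**The concern.** The protocol treats lens contact as important enough to change how a subject is followed, but the analysis population does not use that distinction. What removes a touch-only subject from the Safety Set is an operative adverse event, so membership depends on the outcome being tabulated. In a device trial, events at the moment of delivering the lens are ones a reader would want to compare by arm.

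A listing shows that an event happened but gives no rate by arm. The disposition table gives a count by arm but no event. The screen-failure and replacement rules make these subjects harder to see, because a subject who met the lens and had an event could be labelled a screen failure and replaced by one who had none.

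**Working it through.** **Step 1. Trace a touch-only subject through the visible safety summaries.**

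| Summary | Population | Touch-only subject counted? |
|---|---|---|
| Intraoperative complications (SAP 12) | Safety Set | No |
| Optical surgical interventions, SSIs (SAP 15.1) | Safety Set by default | No |
| Contrast sensitivity (SAP 15.1) | Best Case Set, which also needs an implanted eye | No |
| ISO cumulative and persistent events (SAP 15.2) | Eyes in the Safety Set | No |
| Ocular treatment-emergent event rates (SAP 15.3) | Safety Set by default | No |
| Adverse event listings (SAP 15.3) | All adverse events | Listed, no rate |
| Disposition (SAP 9) | Randomized subjects | Counted, no event rate |

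The ITT Set appears in the visible analyses only as an effectiveness sensitivity analysis (SAP 13.1.2 and its counterpart in 13.2).

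**Step 2. Arm sizes.** SAP 5 gives 501 subjects randomized 2:1: 501 × 2/3 = 334 test and 501/3 = 167 control, matching the stated figures. The plan gives no number of touch-only cases. The event counts below are assumptions.

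**Step 3. Effect of one excluded case that has the tabulated event.** With m events among N in the set, the plan reports m/N. Including the case gives (m + 1)/(N + 1). The difference is (1 − m/N)/(N + 1), so it can never exceed 1/(N + 1).

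- Test, m = 3: 3/334 = 0.898% against 4/335 = 1.194%, a difference of 0.296 points (ceiling 1/335 = 0.299).
- Control, m = 3: 3/167 = 1.796% against 4/168 = 2.381%, a difference of 0.585 points (ceiling 1/168 = 0.595).

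**Step 4. Effect if the excluded case lacks the tabulated event.** The direction reverses and the size is negligible.

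- Test: 3/334 = 0.898% against 3/335 = 0.896%, 0.003 points.
- Control: 3/167 = 1.796% against 3/168 = 1.786%, 0.011 points.

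Step 3 therefore applies to the ocular-event rate, and to the complication rate where the operative event is recorded as a complication. A serious-event rate, a single preferred term or an ISO category moves this way only if the case has that event. Seriousness has its own criteria in Protocol 8.7.2: "A serious adverse event (SAE) is defined as any untoward medical occurrence that meets any of the following".

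**Step 5. Should the Safety Set be widened instead?** Take an assumed 1/334 against 0/167 optical SSIs and the 0.014 margin. The restricted estimates under the null are 0.014 and 0, so z = (1/n − 0.014)/√(0.014 × 0.986/n), where n is the number of test eyes.

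- n = 334: z = −1.712, one-sided p = 0.0434.
- n = 337 (3 test eyes without a study lens added as non-events): z = −1.724, p = 0.0424.
- n = 344 (10 added): z = −1.751, p = 0.0400.

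Eyes that do not carry the lens cannot have an intervention caused by its optics. Adding them only moves the test toward non-inferiority.

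**The case against.** The strongest reply is that the gap is narrow and the data are not lost. Several Protocol 5.3 reasons where contact is likely (haptic misplacement, optic or haptic damage, failure to fixate) suggest a lens already inside the eye. A lens inserted and then removed might count as implanted: SAP 7.2 asks for "all subjects (eyes) with successful IOL implantation with at least one postoperative visit", while SAP 7.4 does not ask for success. All adverse events are listed, operative variables are listed for each eye, and disposition is given by arm. For one or two subjects, a careful reader could reconstruct most of the picture. SAP 7.5 is redacted and the table shells are not shown, so a suitable table may already be planned.

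Much of this stands. The gap is firm only where the lens touched the eye but was not inserted. For a lens inserted and removed, the plan does not settle the matter. The conclusion is limited to the visible text. What does not stand is that listings are a substitute: they give no rate by arm, and the omitted subjects are selected by their event.

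Three stronger readings are tempting, and the documents do not support them.

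- **These subjects vanish from reporting.** They do not: collection, follow-up, listings and disposition all cover them.
- **Every safety rate is understated.** Step 4 shows this holds only for rates whose event the excluded subject has.
- **SAP 9 would count recipients of a non-study lens as implanted.** The wording permits this, but SAP 13.1.2 uses the same phrase and evidently means the study IOL. This is at most a clerical point.

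**Conclusion.** The point holds as a limited gap in safety tabulation. On a plain reading of the visible text, touch-only first-eye cases enter no by-arm safety rate, and they are left out because of an operative adverse event. If such cases occur, the ocular treatment-emergent rate is understated by about 0.3 points per test-arm case, and the complication rate likewise where the event is recorded as a complication. The figure is about 0.6 points per control-arm case, if the rule covers that arm: the operative sentences in Protocol 5.3 speak of the investigational IOL, although the section title speaks of a study IOL.

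These sizes rest on the planned 334 and 167 and on assumed event counts. The number of cases is unknown and may be zero.

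A reader might infer that the Safety Set is wrong for the co-primary SSI test, or that the trial's conclusion is at risk. Neither follows. An implanted-eye denominator suits that test, the affected event and complication tables are descriptive, and no success criterion is shown to change. The priority is low to moderate.

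**What to change.** Leave the Safety Set as it is for the SSI non-inferiority test and the ISO rate comparisons. Add one descriptive table by arm, showing intraoperative complications, ocular treatment-emergent events and ocular treatment-emergent serious events. Its denominator should be all first and second eyes with study-lens contact or attempted implantation, grouped by the lens attempted. It should include any such subject otherwise classed as a screen failure or replaced.

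Basing the table on contact or attempt means that it does not depend on whether a lens inserted and removed counts as implanted. A sentence in SAP 7.4 settling that would still help. The rule should be fixed before unmasking so that exposure is not decided after the events are seen.

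The cost is one extra table. SAP 12 lists no lens-contact item, so a yes/no field may be needed if the operative form has none. A few more events may be reported. Adverse event collection, endpoints, tests and clinical rules do not change.

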#### **7.5 [REDACTED]**

### **8. General Statistical Considerations**

#### **8.1 Unit of Analysis**

The unit of analysis in this study will be the first operative eye for all primary effectiveness and safety summaries, and the unit of analysis will be the second operative eye and all eyes for supportive safety summaries; [REDACTED]

[REDACTED]. Both eyes of each subject will be treated during the study. For those subjects whose eyes are both determined to be eligible for cataract surgery/IOL implantations at Pre-Operative Visit 0, the eye with the worse BCDVA will be scheduled for surgery first. If BCDVA is the same for both eyes, the right eye will be implanted first. Additionally, non-ocular AEs and medical history will be presented at the subject level.

## 8.2 Missing or Inconclusive Data Handling

Missing data for primary and secondary effectiveness analyses will be imputed under the following strategies.

Nonmonotone missing data will be multiply-imputed using treatment-based Markov chain Monte Carlo (MCMC) methods; monotone missing data will be multiply imputed using regression methods assuming data as either missing at random (MAR) or missing not at random (MNAR) as described below.

### Primary Strategy

1. Withdrawal due to physician decision: missing data assumed to be MNAR. Control-based multiple imputations will be completed for superiority hypotheses and treatment-based multiple imputations will be completed for non-inferiority hypotheses. [hypothetical strategy]
2. Missing data without withdrawal or withdrawal due to reasons other than due to physician decision: missing data assumed to be MAR. Treatment-based multiple imputations will be completed. [hypothetical strategy]

### Secondary Strategy (non-inferiority hypotheses only)

1. Withdrawal due to physician decision: missing data assumed to be MNAR. Treatment-based multiple imputations, *using the worst half of the subjects who have data within the same treatment group*, will be completed. [hypothetical strategy]
2. Missing data without withdrawal or withdrawal due to reasons other than due to physician decision: missing data assumed to be MAR. Treatment-based multiple imputations will be completed. [hypothetical strategy]

Partial/missing start and end dates for AEs and concomitant medications will be imputed as follows:

Partial/missing start date:

- Dates with missing day only will be imputed as the 1st of the month unless the month and year are same as the month and year of study lens implantation, in which case missing day will be imputed as the day of study lens implantation.
- Dates with both day and month missing will be imputed as 1 Jan unless the year is same as the year of study lens implantation, in which case missing day and month will be imputed as the first day and month of study lens implantation.
- Completely missing dates will be imputed as the date of study lens implantation unless the end date is on or before the date of study lens implantation, in which case missing date will be imputed as 1 Jan of the same year as the end date.

Partial/missing end date:

- Dates with missing day only will be imputed as the last day of the month.

- Dates with both day and month missing will be imputed as 31 Dec.
- If the ongoing flag is missing or “Yes” then the date will not be imputed. If ongoing is “No” then the missing end date will be imputed as the study completion or discontinuation date.

The original dates will be displayed in data listings and the imputed dates will be used in derivations only (study day, treatment-emergence status, etc).

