### **11.2 Prior and Concomitant Medications**

Prior and concomitant medications will be coded using World Health Organization Drug Dictionary (WHODrug) Global (B3, September 2021) and summarized to the therapeutic drug class (Anatomical Therapeutic Chemical [ATC] 4 classification) and preferred name. If the ATC 4 classification is not provided, then the next highest classification that is provided in the coding dictionary will be used. The preferred name will be defined as the active ingredient; if the active ingredient is not provided or includes more than two ingredients (e.g., multivitamins), then the drug name will be summarized as the preferred name. Prior to database lock, any uncoded terms will be summarized under the ATC classification and preferred name of “Uncoded.”

Prior medications for a respective eye are defined as those medications that start and stop before the operation for the respective eye. Concomitant medications for a respective eye are defined as those medications listed as having been taken (1) prior to the respective eye IOL implantation and continuing for

any period of time following the respective eye implantation or (2) at any time following IOL implantation.

Ocular and non-ocular concomitant medications will be summarized separately at the subject level by treatment group using discrete summary statistics for the Safety Set. Subjects may have more than one medication per ATC text. At each level of subject summarization, a subject will be counted once if he/she reports one or more medications. Percentages will be based on the number of subjects in each treatment group. In the summaries, ATC classes and preferred names within an ATC class will be presented in alphabetical order. Listings of concomitant medications will be generated separately for ocular and non-ocular data.

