### **15.3 Adverse Events**

[figure not shown]
Adverse events (AEs) will be coded using MedDRA Version 24.1.

Non-ocular treatment-emergent adverse events (TEAE) include all AEs occurring or worsening during or after the first eye operation. Ocular TEAEs for a respective eye will include all AEs occurring or worsening during or after the operation for the respective eye.

TEAEs based on consensus definitions as set forth by the American Academy of Ophthalmology (AAO)'s Task Force will be summarized by treatment group using discrete summary statistics. Separate summaries will be provided for first operative eyes, second operative eyes, and all operative eyes.

An overall summary will be presented that includes the number and percentage of subjects who experienced at least one event by treatment group for the following AEs:

- TEAEs
- Ocular TEAEs
- Non-ocular TEAEs
- Treatment-emergent Serious Adverse Events (TE-SAEs)
- Ocular TE-SAEs
- Non-ocular TE-SAEs
- Ocular device-related TEAEs
- Ocular TEAEs by strongest relationship to study device
- Ocular TEAEs by strongest relationship to surgical procedure
- Ocular TE-SAEs by strongest relationship to study device
- Ocular TE-SAEs by strongest relationship to surgical procedure

- Ocular TEAEs of moderate to severe severity
- Ocular TEAEs by maximum severity
- Ocular TEAEs by study day of onset
- Ocular TEAEs by age group (< 65 years vs  $\geq$  65 years)
- Ocular TEAEs by pre-operative photopic pupil size (Small [ $<$  2.5 mm], Medium [2.5 to  $\leq$  4 mm], Large [ $>$  4 mm])
- Ocular TEAEs by site
- TEAEs leading to discontinuation from study
- TEAEs leading to death

For the summary of ocular TEAEs by pupil size, the average pupil size computed over both eyes will be used to determine the pupil size subgroup.

In addition, the following summaries by SOC, PT, and treatment group will be provided at eye level (first operative eyes, second operative eyes, and all operative eyes separately) or subject level as appropriate:

- Ocular TEAEs
- Non-ocular TEAEs
- Ocular TE-SAEs
- Non-ocular TE-SAEs
- Ocular TEAEs related to study device
- Ocular TEAEs related to surgical procedure
- Ocular TEAEs by maximal severity

In the summaries, SOCs are listed in alphabetical order, and PTs within an SOC are listed in order of descending frequency for FINEVISION HP treatment.

[figure not shown]
All AEs and all TE-SAEs will be presented in separate listings.

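### SAP 8.2 moves partial start dates to the implantation date without checking a known end date in two of its three rules, and does not say which eye's implantation is meant

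*SAP*

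**What the plan says.** The partial-date rules stand at the end of SAP 8.2, after the imputation strategies. There are three rules for start dates.

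- **Day missing.** "Dates with missing day only will be imputed as the 1st of the month unless the month and year are same" as those of implantation, "in which case missing day will be imputed as the day of study lens implantation".
- **Day and month missing.** 1 January is used, unless the year is the implantation year, "in which case missing day and month will be imputed as the first day and month of study lens implantation".
- **Start completely missing.** "Completely missing dates will be imputed as the date of study lens implantation unless the end date is on or before the date" of implantation; in that case 1 January of the end-date year is used.

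Section 8.2 then says that "the imputed dates will be used in derivations only (study day, treatment-emergence status, etc").

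These dates feed two eye-level definitions. SAP 15.3: "Ocular TEAEs for a respective eye will include all AEs occurring or worsening during or after the operation for the respective eye". SAP 11.2: "Prior medications for a respective eye are defined as those medications that start and stop before the operation for the respective eye". For non-ocular events, SAP 15.3 takes the first-eye operation as the reference. SAP Table 1 places the second implantation 7 to 30 days after the first.

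**The concern.** There are two gaps.

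**End date.** The condition "unless the end date is on or before the date of study lens implantation" appears only in the third rule. A record with a known month or year is thus protected less than one with no start date at all. Where the known end precedes surgery, the first two rules produce a start later than the end and mark a preoperative event as treatment-emergent.

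Such records can exist. Protocol 8.7.5 collects AEs from consent, Protocol 8.1 allows up to 90 days between the Preoperative Visit and surgery, and Protocol 8.5 records medications from 30 days before that visit.

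**Anchor.** Section 8.2 speaks of lens implantation as a single date, but each subject has two. The programmer must choose, and the choice can alter the second-eye TEAE tables.

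**Working it through.** The documents give no figure to reproduce, so the check applies the rules literally to example dates and then counts over a calendar.

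**Worked cases** (dates invented for illustration)

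1. AE start March 2022, day unknown; end 5 March; surgery 20 March. The month matches, so the start becomes 20 March. End minus start = 5 − 20 = −15 days. The start is on the operation date, so the AE is flagged treatment-emergent.
2. Medication start 2022 only; end 10 February 2022; surgery 20 March. The year matches, so the start becomes 20 March, after the stop. SAP 11.2 needs both start and stop before surgery, so the drug is not prior.
3. Eye A 5 March, eye B 25 March; eye-B AE start March, day unknown. With eye A as anchor the start is 5 March, not treatment-emergent for eye B. With eye B as anchor it is 25 March, treatment-emergent.
4. Eye A 20 March, eye B 10 April; eye-B AE start April, day unknown. With eye A as anchor the month does not match, so the start is 1 April, not treatment-emergent for eye B. With eye B as anchor it is 10 April, treatment-emergent.

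**How often the end-date gap bites, given a partial date**

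Assumptions, not from the documents: surgery dates uniform over a 365-day year; AE onset k = 1 to 90 days before surgery, uniform; the AE ends d days after onset, with the end known. It ends before surgery when k > d, which gives 365 × (90 − d) combinations.

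*Day missing.* The rule fails when onset and surgery share a month. For a month of L days this is (L − d − 1)(L − d)/2 combinations, or zero if L ≤ d + 1. There are seven months of 31 days, four of 30 and one of 28.

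| d | Failing combinations | Total | Share |
|---|---|---|---|
| 1 | 7×435 + 4×406 + 351 = 5,020 | 32,485 | 15.5% |
| 7 | 7×276 + 4×253 + 210 = 3,154 | 30,295 | 10.4% |
| 14 | 7×136 + 4×120 + 91 = 1,523 | 27,740 | 5.5% |
| 30 | 0 | 21,900 | 0% |

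*Day and month missing.* The rule fails when onset and surgery share a year: share = 1 − mean(k)/365, where mean(k) = (d + 91)/2.

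- d = 1: 1 − 46/365 = 87.4%
- d = 30: 1 − 60.5/365 = 83.4%

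**How often the anchor matters, if the first eye were used**

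Take true eye-B events that begin on or after eye-B surgery, in that calendar month, with the day missing, and a gap uniform on 7 to 30 days. The imputed start is either the eye-A date (same month) or the 1st (different month). Both precede eye-B surgery unless that surgery is itself on the 1st. Enumeration gives 93.6% flagged as not treatment-emergent for eye B.

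The two surgeries share a month in (7×300 + 4×276 + 231)/(365 × 24) = 3,435/8,760 = 39.2% of date pairs. Cases 3 and 4 show that the loss occurs in both situations.

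All these percentages are shares of particular partial-date records. None is an expected rate in the study.

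**The case against.** **The effect is conditional.** It needs a partial start in the implantation month or year together with a known earlier end, or a partial second-eye start near the operations. Protocol 8.7.5 asks for an onset date for each AE, and Protocol 10.1.9 provides queries for omissions. This stands, and it keeps the point minor. It does not make the rule correct for the records it does reach.

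**Moving an unclear start to implantation is a usual, conservative convention.** It over-counts treatment-emergent events, and does so by the same rule in both arms. This stands where no end date contradicts the move. It does not justify a start after a known end.

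**The eye-level definitions point to the respective eye.** A programmer deriving an eye-B flag would naturally use eye B's operation. A reader might infer that second-eye events will be lost. The documents do not support that, because the loss follows only if the first eye is chosen. The word 'first' in the year-only rule may hint at the first implantation, but it is unclear and appears in that rule alone. What remains is an unstated anchor.

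**Medications.** A reader might infer that drugs stopped before surgery become concomitant. SAP 11.2 defines concomitant by use continuing past implantation or occurring after it, and a known earlier stop meets neither clause. Such a drug fails 'prior' and may fall into neither class, depending on the programming.

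**Different calendar months.** The two surgeries fall in different months in 60.8% of date pairs. A reader might take this as an error rate. It is not, since misassignment under first-eye anchoring also occurs within one month.

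**Conclusion.** The point holds in limited form. Followed as written, the first two start-date rules in SAP 8.2 give impossible dates and a wrong treatment-emergent flag for events known to have ended before surgery in the implantation month or year. The anchor is also unstated for subjects with two implantations; this is an ambiguity with a possible consequence, not a demonstrated error.

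The number of affected records is unknown and probably small. The shares in the working rest on assumed uniform timing and assumed event durations.

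A reader might infer that the trial's main conclusions are at risk. They are not. The effect is confined to TEAE summaries, study day and medication status. The co-primary effectiveness endpoints and the SSI rate do not use the flag. SAP 15.2 counts ISO cumulative events at any time in the study. All AEs are listed, and listings show the original dates.

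**What to change.** Amend SAP 8.2 as follows.

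1. **First two start-date rules.** If the known end date is strictly before the relevant implantation date, impute the 1st of the month (day missing) or 1 January (day and month missing). Add that a start is never imputed later than a known end.
2. **Third rule.** Change the check from on-or-before to strictly before implantation. SAP 15.3 counts events occurring during the operation. An event that resolves on the day of surgery should therefore stay treatment-emergent; the present check would move its missing start to 1 January. For the same reason, the present check should not simply be copied into the first two rules.
3. **Anchor.** State that it is the respective eye's operation for ocular AEs and for medication status as in SAP 11.2, and the first-eye operation for non-ocular AEs as in SAP 15.3.

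With these changes, case 1 starts on 1 March and is not treatment-emergent. Case 2 starts on 1 January and is prior. Cases 3 and 4 start on 25 March and 10 April and are treatment-emergent for eye B.

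The cost is a few sentences and a small programming change. No data collection changes.
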